9.4.5 Physical Examination, Height, and Weight

A physical examination which includes examination of head, eyes, ears, nose, and throat (HEENT); neck; cardiovascular; lungs; abdomen; extremities; skin; lymph nodes; and musculoskeletal, will be conducted for all patients during the Baseline Visit (Day 1). Height and weight are to be measured at the Baseline Visit. A targeted physical

examination at the TOC Visit is only needed per the Investigator's discretion if a reported AE requires further evaluation.

9.4.6 Pelvic Examination, Vaginal Discharge Assessment and Testing

A pelvic examination including vaginal discharge assessment and testing, will be performed at the Baseline Visit (Day 1) and TOC Visit (and at the follow-up visits, if needed). A non-lubricated speculum must be used during the pelvic examination. Components of the pelvic examination are specified in the following sections.

Prior to enrollment, if any test result is considered exclusionary it is not required to complete the evaluation of any additional samples.

9.4.7 Vaginal Discharge Assessment

During the pelvic examination, conduct clinical assessment of trichomoniasis symptoms (e.g., itching, discharge, odor) (record as Normal, or Abnormal consistent with TV, or Abnormal Other).

9.4.8 Vaginal Discharge Testing

Vaginal discharge testing will be performed at baseline and on each scheduled study day as indicated in the Schedule of Assessments, Table 1.

9.4.8.1 Trichomonas vaginalis

OSOM® Trichomonas Rapid Test - Sekisui Diagnostics

The presence or absence of *T. vaginalis* will be determined by the Investigator, or designee using the OSOM® Trichomonas Rapid Test kit. Commercial test kits will be provided to the sites, and testing will be performed as described in the test instructions (refer to laboratory manual for instructions).

The OSOM® Trichomonas Rapid Test will only be used at Visit 1 (baseline) to determine study eligibility. The OSOM test is not needed if patient qualifies for the study based on a positive NAAT test within 30 days of screening for which treatment has not been initiated.

Patients must have a diagnosis of trichomoniasis at the screening visit as determined by one of the following test results:

- i. have positive NAAT test within 30 days of screening for which treatment has not been initiated (NAAT test results must be available in the patient chart).
- ii. wet mount assessment;
- iii. OSOM® rapid test; note OSOM test not needed if patient has positive NAAT test within 30 days of screening for which treatment has not been initiated.

InPouch™ TV (*Trichomonas vaginalis*) - BioMed Diagnostics, Inc.

The InPouch™ TV test will be utilized to determine the presence or absence of *Trichomonas vaginalis*. Commercial test kits will be provided to the sites, and vaginal samples will be obtained from the posterior fornix of the vagina by the Investigator, or trained designee according to the manufacturer's instructions. Specimens will be sent to a central laboratory. Detailed procedures for sample collection, analysis, and reporting will

be provided in a separate laboratory manual.

9.4.8.2 Wet Mount

Wet mount assessments will be performed at the Baseline Visit (Day 1). Additional, vaginal wet mount testing may be conducted at Visit 3 for further evaluation of trichomoniasis (See Table 1, Schedule of Assessments).

9.4.8.2.1 *Preparation of Slides for Vaginal Saline Wet Mount and Whiff Test*

Using sterile polyester-tipped swabs, swab the lateral vaginal walls with a polyester -tipped applicator and place polyester tip in a tube with approximately 6 drops of saline (~100 μ l; enough to keep the swab moist, but not dilute the sample). Remove the swab from the tube and place a liberal amount of discharge on each of the two glass slides immediately before testing as follows:

9.4.8.2.2 *Slide #1 – KOH Whiff Test*

The Investigator, or designee, will mix approximately two drops of 10% potassium hydroxide (KOH) with the vaginal discharge sample and immediately smell the slide (Note: the assessor should not have any impairment to the sense of smell).

- Assess for a fishy, amine-like odor (record as Positive or Negative; note that a Positive result indicates the presence of the odor). Note: patients with bacterial vaginosis (BV) are eligible for this study.

9.4.8.2.3 *Slide #2 –Vaginal Saline Wet Mount*

The Investigator, or designee, will examine the second vaginal sample slide under a light microscope at 100X magnification and at 400X magnification. Examine for the presence or absence of clue cells and motile trichomonads,

- **Clue cells:** A minimum of 5 representative fields containing squamous epithelial cells should be examined and the ratio of clue cells to vaginal epithelial cells determined at 400X magnification. Clue cells will be identified as vaginal epithelial cells with such a heavy coating of bacteria surrounding them their peripheral borders are obscured. Record clue cells as \geq 20% of the total epithelial cells, or < 20% of the total epithelial cells.
- **Trichomonads:** Record motile trichomonads as Present or Absent.

9.4.8.3 Vaginal pH

The pH of a vaginal sample will be obtained by the Investigator, or designee, at the Baseline Visit (Day 1) only, and the result will be recorded (recorded as < 4.7 or \geq 4.7). The necessary materials and instructions will be provided for vaginal pH testing (refer to laboratory manual for instructions).

9.4.8.4 Sexually-transmitted Infection (STI) Assessments

Assessments for the presence of *Neisseria gonorrhoeae* and *Chlamydia trachomatis* will be performed at the Baseline Visit (Day 1). Patients with positive STI results from the baseline visit should remain in the study and complete all specified procedures. An unscheduled visit may be conducted in order to avoid unnecessary delays in treatment.

Commercial test kits will be provided to the sites, and endocervical samples will be obtained by the Investigator, or trained designee according to the manufacturer's instructions. Specimens will be sent to a central laboratory. The necessary materials and instructions will be provided for STI testing (refer to laboratory manual for instructions).

9.5 INVESTIGATOR'S CLINICAL ASSESSMENT

At Visit 3 (if needed) the Investigator will answer the following question "In your opinion, does the patient require additional treatment for *T. vaginalis* infection at this time? The response will be recorded as Yes or No. If the answer is Yes, the patient will be offered a prescription for a post-study treatment by the Investigator and followed-up outside of the study as they deem clinically necessary.

10. SAFETY AND PHARMACOVIGILANCE

10.1 DEFINITION OF AN ADVERSE EVENT

An AE is defined as any untoward medical occurrence in a clinical trial patient administered a medicinal product and which does not necessarily have a causal relationship with the treatment.

An AE can therefore be any unfavorable and unintended sign (including an abnormal laboratory finding), symptom, or disease temporally associated with the use of an investigational medicinal product, whether or not considered related to the investigational medicinal product.

A new medical condition or the worsening of a pre-existing condition will be considered an AE. Stable chronic medical conditions such as arthritis that are present prior to study entry and do not worsen during the study will not be considered AEs. Worsening of the disease under study should only be recorded as an AE if the outcome is more serious than would normally be expected from the normal course of the disease in a particular patient.

In the study, any event occurring after the clinical trial subject has signed the study Informed Consent (ICF) should be recorded and reported as an AE. Those events occurring prior to drug administration will be considered to be “Non-Treatment-Emergent” AEs and those occurring after drug administration as “Treatment-Emergent” AEs.

10.2 INTENSITY OF ADVERSE EVENTS

The intensity or severity of the AE will be characterized as:

- Mild: AE which is easily tolerated
- Moderate: AE sufficiently discomforting to interfere with daily activity
- Severe: AE which prevents normal daily activities

The maximum severity for the event should be listed when the intensity changes during the course of an AE. If the change in severity represents distinct events rather than a single event, this should be recorded as separate AEs.

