5. STUDY DESIGN

5.1 OVERALL STUDY DESIGN

This is a Phase 3, multi-center, prospective, randomized, placebo-controlled, delayed treatment, double-blind, study to evaluate the effectiveness, and safety of a single, oral dose of Solosec containing 2 grams of secnidazole in female patients with trichomoniasis. Approximately 144 patients who test positive for trichomonas on OSOM® rapid test or via wet mount assessment or have positive *T. vaginalis* NAAT test within 30 days of screening (and have not been treated) and fulfill other eligibility criteria at the baseline visit will be enrolled in this study. The diagnosis of *T. vaginalis* will be confirmed by a positive culture for *T. vaginalis*. The study will consist of a primary study phase (Visit 1 (baseline) to Visit 2 (Day 6-12)) and a follow-up phase (Visit 2 to Visit 3 (7-12 days post Visit 2)). During the primary phase patients will be randomly assigned in a 1:1 ratio to either Solosec or placebo. The randomization will be stratified by site and based on the clinical symptoms of trichomoniasis (present or absent). Patients will return to the clinic for the “test of cure” (TOC) visit to be conducted on Days 6-12 (Visit 2). After all Visit 2 (V2) study procedures have been completed, patients will receive the opposite treatment (placebo patients will receive Solosec and vice versa). Patients with V2 cultures that are subsequently positive for *T. vaginalis* will return to the clinic for Visit 3 (V3) assessments and investigator assessment of need for additional therapy (an additional Visit 4 may be scheduled at the investigator’s discretion if culture at V3 is positive). Patients with cultures that are negative at V2 will be contacted by phone and discharged from the study (no V3 required). A Schedule of Assessments is provided in Table 1.

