9.3.2 Visit 2/Test of Cure Visit (Study Day 6-12)

The Test of Cure (TOC) Visit should be conducted between Study Day 6 and 12.

The following procedures will be performed at the TOC Visit:

1. Assess for adverse events;
2. Review and record concomitant medications/treatments taken during the study;
3. Perform a urine pregnancy test;
4. Perform a targeted physical examination as needed to assess AEs. Collect vital signs;
5. Perform a pelvic examination including assessment of vaginal discharge, and collection of vaginal samples as follows:
 - a. Perform clinical assessment of trichomoniasis genital symptoms (e.g., itching, discharge, odor).
 - b. Collect vaginal sample for *T. vaginalis* testing via:
 - i. BioMed InPouch™ TV test.

Upon completion of the primary phase (Visit 1 (baseline) to Visit 2 (Day 6-12)), the site will use IWRS to receive the Visit 2 kit number for the opposite treatment (placebo patients will receive Solosec and vice versa). Study treatment will be provided for the follow-up phase as described in section in Section 7 of the protocol.

The following procedures will be performed after the patient has been successfully completed the Day 6-12 TOC procedures described above:

1. The patient will self-administer the study medication (without regard to meals). (See Section 7.1 for drug administration instructions).

Patients with negative cultures for *T. vaginalis* at Visit 2 (i.e., negative InPouch™ TV test) will be contacted by phone and discharged from the study (no Visit 3 required). Note: The telephone contact will include an assessment of safety and well-being. Subjects reporting any complaints, or an adverse event will be asked to return for an unscheduled visit for evaluation and safety assessment.

A follow-up visit will be scheduled for all patients who have positive cultures for *T. vaginalis* (i.e., positive InPouch™ TV test at Visit 2).

Note: patients who are subsequently found to have a negative culture for *T. vaginalis* (i.e., negative InPouch™ TV test) from the sample obtained at the Baseline Visit (Day 1) should remain in the study and complete all appropriate study visits.

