## 2. STATISTICAL METHODOLOGY

### 2.1 General Principles

All analyses will be performed using SAS® software version 9.4. Prior and concomitant medications will be coded using World Health Organization (WHO) Drug Dictionary Enhanced March 2019. Medical history and Adverse Events (AEs) will be coded using Medical Dictionary for Regulatory Activities (MedDRA) version 22.0.

Continuous variables will be summarized by n (number of patients with non-missing results), mean, standard deviation (SD), median, minimum, and maximum. Categorical variables will be summarized by count and percent (of patients in the population with a non-missing result).

All data collected will be presented in data listings. Data collected subsequent to TOC (Visits 3 and 4) will be included in data listings but will not be used for any analyses.

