## 2.3 Study Populations

**Intent-to-Treat (ITT):** The ITT population will include all randomized patients. Patients will be summarized based on the randomized treatment group.

**Modified Intent-To-Treat (mITT):** The mITT population will include all randomized patients who were culture positive for *T. vaginalis* and negative for STIs (lab results will not be known until after randomization). Patients will be summarized based on the randomized treatment group.

**Per-Protocol (PP):** The PP population will be composed of patients in the mITT population with consideration of the following criteria: received the study medication as randomized, met inclusion and exclusion criteria, had a TOC visit between Days 6-12, and had no major protocol violations. The composition of the PP population will be finalized and documented in a review of the data conducted prior to unblinding the study database.

**Safety:** The Safety population will be composed of all randomized patients who received any amount of study medication. Patients will be summarized based on the treatment group actually received.

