### **2.6.1 Adverse Events**

AEs that occur through the TOC Visit will be summarized by System Organ Class (SOC), Preferred Term, intensity, and treatment group for treatment-emergent AEs. Summaries will also be provided for study drug-related AEs, serious AEs, and AEs leading to study discontinuation. Each patient will be counted only once for each of the incidence rates, regardless of the number of occurrences (events) the patient experiences.

A Treatment-emergent AE is defined as any AE that occurs after administration of the study drug and through the final visit, or any event that is considered study drug-related regardless of the start date of the event.

	SEC-WH-301 Statistical Analysis Plan	Revision No.: 2.0
	Document Date: 20-Mar-2020	Page 11 of 12

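### An AE that worsens after the Visit 2 switch can be tabulated under the first treatment with a grade reached on the second

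*Protocol*

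**What the plan says.** **Recording.** Protocol 10.2 states: "The maximum severity for the event should be listed when the intensity changes during the course of an AE". The next sentence adds an exception: "If the change in severity represents distinct events rather than a single event, this should be recorded as separate AEs". Protocol 10.4 lists what is assessed for each AE (onset, duration, intensity, causality) and has AEs followed until they resolve or another listed end point is reached. A date of grade change is not in that list.

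**Switch.** Protocol 5.1 says that after the Visit 2 procedures "patients will receive the opposite treatment (placebo patients will receive Solosec and vice versa". Protocol 9.3.2 implements this through the randomization system at the same visit.

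**Tabulation.** SAP 2.6.1: "AEs that occur through the TOC Visit will be summarized by System Organ Class (SOC), Preferred Term, intensity, and treatment group for treatment-emergent AEs". SAP 2.3 says of the Safety population: "Patients will be summarized based on the treatment group actually received". It does not name the phase. Because the tables stop at TOC, I read the column as the first treatment.

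**Exclusion of later data.** SAP 2.1: "Data collected subsequent to TOC (Visits 3 and 4) will be included in data listings but will not be used for any analyses". SAP section 4 repeats this as a clarification of the protocol.

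**The concern.** The SAP's cut-off chooses which AEs enter the table. It does not say as of when their grade is read. An AE that starts on the first product belongs in that product's column, so its onset is correctly placed. If it is still present when the second product is taken and then worsens as the same event, the record holds one grade, and that grade was reached on the other product. Ending the AE window at the second dose would not repair this, because the onset already lies inside the window.

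Intensity is one of the stated bases of the safety evaluation (Protocol 11.5.2, SAP 2.6). In a placebo-first patient, the placebo column could carry a grade reached after Solosec. The table would also contain information that SAP 2.1 means to leave out.

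**Working it through.** The plan gives no figure on this point, so the check is mainly a trace of the rules, followed by an illustration of size.

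**1. Trace for one AE.** Take a placebo-first patient with a mild headache starting before Visit 2.
- At Visit 2 the headache is ongoing and the patient takes Solosec.
- The headache becomes severe and the investigator regards it as the same event. Protocol 10.2 then calls for one record graded severe.
- Onset is before TOC, so SAP 2.6.1 selects the record and tabulates its intensity under placebo.
- SAP 2.1 would bar the later grade, but a record that holds only the maximum has no earlier grade to fall back on.

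**2. Does other text fix the grade at the second dose?**
- Protocol 10.1 counts worsening of a pre-existing condition as an AE, but the sentence that follows concerns conditions present before study entry.
- Protocol 11.5.2 covers events present at baseline that worsen. The treatment-emergent definition in SAP 2.6.1 does not include that limb.
- SAP 3.1 sets baseline by a single dosing day, Day 1, so there is no second-period baseline.
- The exclusion in SAP 2.1 names Visits 3 and 4. Patients with a negative Visit 2 culture are followed by telephone and, if needed, an unscheduled visit (Protocol 9.3.2, 9.3.4), which that parenthesis does not mention.

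None of these fixes the grade at the Visit 2 dose.

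**3. Size.** Inputs from the documents: about 144 enrolled (Protocol 11.2), 1:1 allocation (Protocol 5.1). Placebo-first patients: 144 / 2 = 72. The documents do not give q, the share with an AE ongoing at Visit 2, or w, the share of those that worsen afterwards as one event. Both are assumptions. Affected patients = 72 × q × w:

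| q | w = 10% | w = 25% | w = 50% |
|---|---|---|---|
| 2% | 0.14 | 0.36 | 0.72 |
| 5% | 0.36 | 0.90 | 1.80 |
| 10% | 0.72 | 1.80 | 3.60 |

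The range is about 0.1 to 3.6 patients. It takes all 72 as dosed at Visit 2, so it is slightly high if some drop out first.

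**4. Who is seen again.** Only patients with a positive Visit 2 culture attend Visit 3. At the planning cure rates of 40% and 75%, and counting every non-cure as a positive culture, that is 50 × 0.60 = 30 placebo-first and 50 × 0.25 = 12.5 Solosec-first mITT patients. More AE updates at a clinic visit after the switch would come from the placebo-first arm.

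**The case against.** The strongest reply is that existing text already covers the case. Worsening after a second, different dose is a natural candidate for a distinct event, and Protocol 10.2 sends distinct events to separate records. SAP 2.1 bars post-TOC data from analysis, so on a strict reading a grade first reached after the switch is not analysis data. What remains would be whether the grade at TOC can be recovered. That depends on the eCRF, its completion guideline and the data management plan, none of which is available here.

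Much of this stands. The two provisions narrow the problem, and if the eCRF dates grade changes the SAP exclusion can be carried out. They do not close it: whether a change is distinct is left to judgement and is not tied to the second dose, and Protocol 10.4 does not call for a dated grade.

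It also stands that the effect is limited. AE incidence and the primary endpoint are untouched, no formal between-arm safety test is planned, and AEs spanning Visit 2 can be identified in the listings from onset and duration.

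A reader might infer that the rule flatters Solosec, because drug-caused worsening after the switch can fall only in the placebo-first arm, and that arm is seen more often at Visit 3. The documents do not establish this. Natural-course worsening after Visit 2 would load onto the Solosec column for Solosec-first patients. With nausea, headache, dysgeusia and vaginal yeast infections reported for Solosec (Protocol 3.2.1), that arm may also have more AEs ongoing at Visit 2 and so open to regrading.

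**Conclusion.** The point holds as a gap between recording and tabulation. Followed as written, the rules can put a post-switch grade in the first-treatment column, contrary to the intent of SAP 2.1. It concerns the intensity of the few AEs ongoing across the Visit 2 dose: about 0.1 to 3.6 placebo-first patients if 2% to 10% have such an AE and 10% to 50% of those worsen as one event. Those rates are assumed. The net direction between arms is undetermined.

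A reader might go further and infer that the placebo count of severe AEs could double. Protocol 3.2.1 mentions 9 severe AEs and 518 Solosec-treated women with bacterial vaginosis; 9 / 518 = 1.74%, and 72 × 1.74% = 1.25. That comparison fails on three counts:
- The 0.1 to 3.6 counts worsening to any grade. If 10% to 30% of worsenings reached severe (again an assumption), the count would be 0.14 × 0.10 = 0.01 to 3.6 × 0.30 = 1.08, reaching one patient only when every assumption is at its top.
- 1.74% is a Solosec rate in another disease, and the documents give no placebo rate of severe AEs.
- The protocol reports the 9 events across the bacterial vaginosis studies and does not clearly tie all of them to the 518 women.

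**What to change.** - **SAP 2.6.1:** state that the intensity tabulated for AEs occurring through TOC is the maximum reached before the Visit 2 dose. The cut should be the dose and not the visit date, since the dose is given at that visit after its procedures.
- **Protocol 10.2 or the eCRF completion guideline:** state that for an AE ongoing at Visit 2 the maximum grade up to that dose is recorded, and that any later worsening is entered as a new record with its own onset date. This makes the SAP rule executable.

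If the eCRF already dates grade changes, the SAP sentence alone is enough.

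The cost is about two sentences and a few extra AE records, some of which will split what is clinically one event. Those later records start after the dose and should stay out of the through-TOC tables. Changing the protocol text itself needs sponsor and IRB/IEC approval (Protocol 12.2); using the completion guideline leaves the protocol text unchanged.

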10.3 RELATIONSHIP OF ADVERSE EVENTS TO STUDY DRUG

The causal relationship of the investigational product to the AE(s) should be characterized as:

Not Related: There is *no reasonable possibility* that the AE was caused by or attributed to the investigational product

Related: There is a *reasonable possibility* that the AE was caused by or attributed to the investigational product. A causal relationship cannot be ruled out.

